# 5.2. Complement and APL-9 Background

Complement proteins exist in systemic circulation at high concentrations and can undergo rapid activation in response to infection or tissue damage, triggering local and systemic inflammation.

The complement system is composed of 3 activation pathways: classical, lectin, and alternative. Initiation of each pathway generates proteolytic enzyme complexes (C3 or C5 convertases) that cleave peptide bonds in the C3 and C5 proteins. The C3 protein is central to the activation of all 3 pathways of the complement cascade. Proteolytic cleavage of C3 releases the anaphylatoxin C3a and activates C3b, which with the factor B fragment Bb forms C3bBb, an enzyme complex (C3 convertase) with the ability to cleave C3. The C4 protein plays a role in both the classical and lectin pathways of complement activation. Following activation of these pathways, proteolytic enzyme complexes cleave a peptide bond in C4, releasing the anaphylatoxin C4a and activating C4b, which assembles with C2b to form a different C3 convertase, C2bC4b. Downstream of C3 activation, the cleavage of the C5 protein results in the production of the anaphylatoxin C5a and C5b, leading to the formation of the surface-bound membrane attack complex (C5b-9) or its soluble form, the TCC.

APL-9 contains 2 cyclic pentadecapeptides covalently attached at the ends of a 10-kDa linear poly(ethylene glycol) chain. The cyclic peptides bind and inhibit C3 and its C3b fragment and are responsible for the bioactivity of APL-9. The compound is a potent inhibitor of all 3 complement activation pathways and blocks the formation of most associated effector functions, including formation of the membrane attack complex.

In a Phase 1, double-blind, randomized, placebo-controlled, single ascending dose study in healthy volunteers (Study APL9-101), 24 subjects were treated with a single dose of IV APL-9 and 10 subjects were treated with matching placebo. The results of this study confirmed the potent inhibition of complement and established the pharmacokinetic (PK) profile; no significant safety findings were observed.

APL-9 is manufactured under current Good Manufacturing Practices as outlined in the US Code of Federal Regulations (21 CFR §210, 211) and the International Council for Harmonisation of Technical Requirements for Pharmaceuticals for Human Use (ICH Q7).

More detailed descriptions of the chemistry, pharmacology, efficacy, and safety of APL-9 can be found in the APL-9 Investigator's Brochure.

# 5.3. Benefit-Risk Assessment

This is an interventional study in COVID-19 subjects with respiratory failure, including mild to moderate ARDS, a life-threatening complication of SARS-CoV-2 infection. Based on the known pathological role of complement overactivation in ARDS, C3 inhibition by APL-9 may improve pulmonary function in subjects with COVID-19. If efficacious, APL-9 may also reduce COVID-19-associated morbidity and mortality and shorten the length of stay in intensive care and respiratory units, which may be in critical shortage during outbreaks.

Nonclinical studies of SARS-CoV-1 have indicated that complement inhibition had beneficial effects to reduce lung inflammation, and a healthy volunteer clinical study of IV APL-9, a C3 inhibitor, demonstrated acceptable PK and safety profiles. Subjects participating in this study will also receive SOC therapy independent from randomization.

The risks include local adverse effects from IV dosing, adverse effects that are currently unknown, additional infections secondary to COVID-19, possible increased risk of bacterial infection due to complement inhibition, and possible lack of efficacy. All subjects who are to receive study drug treatment will also receive a broad-spectrum antibiotic (see Section 9.5) to counter the theoretical concern of increased risk of bacterial infection due to complement inhibition. As a further subject safety mechanism, the study will initially enroll and treat 6 subjects in an open-label fashion with APL-9 (Part 1). A data monitoring committee (DMC) will review the clinical data collected in Part 1 before Part 2 of the study will be initiated. Required criteria for initiation of Part 2 will include (1) no fatal/life-threatening serious adverse events (SAEs) thought possibly related to APL-9 by the DMC, and (2) no more than 1 subject requiring premature treatment discontinuation by the investigator due to adverse events (AEs) or abnormal laboratory tests. After Part 2 is initiated, the DMC will perform further reviews of clinical data after the 10th and 30th subjects have reached the approved treatment duration, discontinuation of respiratory support (oxygen supplementation or mechanical ventilation), or hospital discharge, whichever occurs latest.

# 6. **OBJECTIVES AND ENDPOINTS**

## 6.1. **Objectives**

## 6.1.1. Primary Objective

The primary objective of this study is to evaluate the safety of APL-9 compared with that of vehicle control (as add-on therapy to SOC) in subjects with COVID-19 who have respiratory failure, including mild to moderate ARDS.

## 6.1.2. Secondary Objectives

The secondary objectives of this study are to evaluate the effect of APL-9 on:

- Hospital length of stay
- Overall survival
- Change in Sequential Organ Failure Assessment (SOFA) score
- Time on mechanical ventilation
- Time on oxygen therapy
- APL-9 PK
- APL-9 pharmacodynamics (PD; the effect of APL-9 on complement, coagulation, and inflammation biomarkers)

## 6.1.3. Exploratory Objectives

The exploratory objectives of this study are to evaluate:

- The effect of APL-9 on presence of active SARS-CoV-2 infection
- The effect of APL-9 on new oxygen use during the study (reinitiation 24 hours or more after cessation of prior oxygen therapy)
- The effect of APL-9 on new mechanical ventilation use (reinitiation 24 hours or more after cessation of prior mechanical ventilation)
- CCI

## 6.2. Endpoints

## 6.2.1. Primary Objective Endpoint

• Cumulative incidence of treatment-emergent SAEs and treatment-emergent adverse events (TEAEs)

## 6.2.2. Secondary Objective Endpoints

- Hospital length of stay (measured in days)
- Any-cause mortality (measured from beginning of treatment until the safety follow-up assessment 30 days after last study treatment [up to and including Study Day 51 with a +7-day window])
- SOFA score
- Total duration of mechanical intervention (measured in days)
- Total duration of oxygen therapy (by continuously worn mask or nasal cannula, measured in days)
- APL-9 PK parameters
- Observed values and changes from baseline in markers of complement activation (C3, C3a, C4, C4a, Bb, C5a, TCC, and alternative complement pathway hemolytic activity [AH50]), coagulopathy (reticulocyte count, schistocytes, lactate dehydrogenase, D-dimer, ferritin, haptoglobin, and fibrinogen), and inflammatory cytokines (C-reactive protein [CRP], tumor necrosis factor α [TNFα], IL-1β, and IL-6).

## 6.2.3. Exploratory Objective Endpoints

- Incidence, duration, and extent of new supplemental oxygen use (reinitiation 24 hours or more after cessation of prior supplemental oxygen therapy)
- Incidence, duration, and extent of new mechanical ventilation use (reinitiation 24 hours or more after cessation of prior mechanical ventilation)
- CCI
- Presence of active SARS-CoV-2 infection at the end-of-treatment visit. Presence of SARS-CoV-2 viral RNA or viral antigen may be detected in respiratory specimens (collected using nasopharyngeal or oropharyngeal swabs) with a qualitative nucleic acid amplification test (such as reverse transcriptase polymerase chain reaction [RT-PCR]), viral antigen test, or other diagnostic method that is authorized, cleared, or approved by the US Food and Drug Administration (or equivalent local authority) for SARS-CoV-2 viral detection. Serology-based antibody tests do not detect the presence of virus and therefore are not considered diagnostic and cannot be used for study eligibility screening or for subsequent SARS-CoV-2 assessments.

# 7. STUDY DESIGN

# 7.1. Overall Study Design

This Phase 1/2 trial includes an initial open-label period (Part 1) before proceeding to a randomized, double-blind, vehicle-controlled, parallel-group period (Part 2). Part 1 of the study is designed to evaluate the safety of open-label APL-9 with SOC in a small number of subjects who have respiratory failure (including mild to moderate ARDS) due to COVID-19 and who require respiratory support (supplemental oxygen or mechanical ventilation). A DMC will analyze the data for Part 1 and decide whether Part 2 of the study will be initiated. Required criteria for initiation of Part 2 will include (1) no fatal/life-threatening SAEs thought possibly related to APL-9 by the DMC, and (2) no more than 1 subject requiring premature treatment discontinuation by the investigator due to AEs or abnormal laboratory tests. Part 2 of the study is designed to evaluate the safety and efficacy of APL-9 with SOC compared with those of vehicle with SOC in a larger number of subjects who have respiratory failure (including mild to moderate ARDS) due to COVID-19 and who require respiratory tests. Part 2 of the study is designed to evaluate the safety and efficacy of APL-9 with SOC compared with those of vehicle with SOC in a larger number of subjects who have respiratory support (supplemental oxygen or mechanical ventilation).

Subjects will participate only in either Part 1 or Part 2 of the study (ie, subjects who participate in Part 1 of the study will not participate in Part 2).

Further details on the study design for each part of the study are provided below.

## Part 1 (Open-Label Period):

Initially, a cohort of 6 subjects will receive open-label treatment with APL-9 as add-on therapy to SOC (CDC 2020) from Day 1 through Day 7 or resolution of ARDS (PaO2 [partial pressure of oxygen]/FiO2 [fraction of inspired oxygen] ratio >300 mm Hg), whichever occurs earlier. Resolution of ARDS in this study is defined according to the Berlin definition as PaO2/FiO2 ratio >300 mm Hg (ARDS Definition Task Force 2012).

An independent DMC will review the clinical data available for all 6 subjects once the last subject in Part 1 reaches Day 7 or is discharged following the resolution of ARDS (PaO2/FiO2 ratio >300 mm Hg). The DMC will recommend to the sponsor whether:

- the study can proceed to Part 2, and
- the maximum allowed treatment duration in Part 2 can be extended (The DMC can extend the treatment duration beyond Day 7 up to and including Day 21; refer to Part 2 [Randomized Double-Blind Period]).

Follow-up safety assessments for each subject will be collected 30 days following the last dose of APL-9 (with a +7-day window). These assessments will be conducted via inpatient assessment (for subjects still hospitalized) or by telephone call (for subjects discharged).

## Part 2 (Randomized Double-Blind Period):

Part 2 of the study will be initiated only upon recommendation from the DMC. Required criteria for initiation of Part 2 will include (1) no fatal/life-threatening SAEs thought possibly related to APL-9 by the DMC, and (2) no more than 1 subject requiring premature treatment discontinuation by the investigator due to AEs or abnormal laboratory tests. All subjects will receive SOC independent of their randomization. Approximately 60 subjects will be randomly

assigned in a 1:1 ratio to blinded treatment with either APL-9 or saline vehicle. Subjects will receive treatment with APL-9 or vehicle from Day 1 through Day 7, discontinuation of respiratory support (supplemental oxygen or mechanical ventilation), or hospital discharge, whichever occurs latest.

Subjects may receive treatment beyond Day 7 if the DMC approves an extended treatment duration following the review of data from Part 1 or during the conduct of Part 2. The DMC may approve any extended treatment duration up to and including Day 21; extended treatment will be allowed only in subjects who still require respiratory support (oxygen supplementation or mechanical ventilation) at Day 7 with an improved PaO2/FiO2 ratio of at least 20 mm Hg from baseline if arterial blood gas (ABG) test results are available for comparison. If ABG test results are not available, an improvement in FiO2 of at least 4% in nonventilated patients (eg, those on nasal cannula) and 10% in mechanically ventilated patients is needed. FiO2 should be weaned following the site's protocol to keep oxygen saturation at 89% or above. Treatment beyond Day 7 and through any DMC-approved extension will be at the discretion of the investigator. Treatment beyond Day 7 and up to and including any DMC-approved extension will be at the discretion of the investigator.

Follow-up safety assessments for each subject will be collected 30 days following the last dose of study treatment (up to and including Study Day 51 with a +7-day window). Safety assessments may be performed any time during the 30-day follow-up period at the investigator's discretion but are required 30 days after the last dose of study drug (up to and including Study Day 51 with a +7-day window). These assessments will be conducted via inpatient assessment (for subjects still hospitalized) or by telephone call (for subjects discharged).

The DMC will perform safety and efficacy data reviews on an ongoing basis during Part 2. Two reviews will be required in Part 2:

- 1. After the 10th subject reaches the approved treatment duration, discontinuation of respiratory support (oxygen supplementation or mechanical ventilation), or hospital discharge, whichever occurs latest
- 2. After the 30th subject reaches the approved treatment duration, discontinuation of respiratory support (oxygen supplementation or mechanical ventilation), or hospital discharge, whichever occurs latest

If the DMC approves an extended treatment period following Part 1 or at any time through the conduct of Part 2, the DMC's safety and efficacy data reviews will be initiated when the 10th and 30th subjects reach the approved extended treatment duration, discontinuation of respiratory support (oxygen supplementation or mechanical ventilation), or hospital discharge, whichever occurs latest. For example, if, following Part 1, the DMC approves treatment up to and including Day 14 in Part 2, the DMC will be required to review safety and efficacy after the first 10 subjects reach Day 14 of treatment, discontinuation of respiratory support (oxygen supplementation), or hospital discharge, whichever occurs latest. Enrollment will not be suspended during the DMC reviews.

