Treatment duration in Part 2 may be maximally extended up to and including Day 21; extended treatment will be allowed only in subjects who still require respiratory support (oxygen supplementation or mechanical ventilation) at Day 7 with a  $PaO_2/FiO_2$  ratio improved by at least 20 mm Hg from baseline if an ABG test result is available for comparison. If an ABG test result is not available, an improvement in FiO2 of at least 4% in nonventilated subjects (eg, those on nasal cannula) and 10% in mechanically ventilated subjects is needed. FiO2 should be weaned following the site's protocol to keep oxygen saturation at 89% or above. Treatment beyond Day 7 and up to and including any DMC-approved extension will be at the discretion of the investigator.

Through the conduct of the study the DMC can recommend any changes to the protocol, including study termination for safety or futility reasons.

3.	TABLE OF CONTENTS, LIST OF TABLES, AND LIST OF
	FIGURES

1.		TITLE PAGE	1
AP	PROVA	L SIGNATURE	2
IN	VESTIC	ATOR'S AGREEMENT	3
PR	отосс	DL AMENDMENT SUMMARY OF CHANGES	4
2.		SYNOPSIS	10
3.		TABLE OF CONTENTS, LIST OF TABLES, AND LIST OF FIGURES	15
4.		LIST OF ABBREVIATIONS AND DEFINITIONS OF TERMS	20
5.		INTRODUCTION	22
	5.1.	Study Rationale	22
	5.2.	Complement and APL-9 Background	23
	5.3.	Benefit-Risk Assessment	23
6.		OBJECTIVES AND ENDPOINTS	25
	6.1.	Objectives	25
	6.1	1. Primary Objective	25
	6.1	2. Secondary Objectives	25
	6.1	3. Exploratory Objectives	25
	6.2.	Endpoints	25
	6.2.	1. Primary Objective Endpoint	25
	6.2.	2. Secondary Objective Endpoints	26
	6.2.	3. Exploratory Objective Endpoints	
7.		STUDY DESIGN	27
	7.1.	Overall Study Design	27
	7.2.	Scientific Rationale for Study Design	
	7.3.	Justification for Dose	
	7.4.	End of Study Definition	29
	7.5.	Study Design and Schedule of Assessments	
8.		STUDY POPULATION	
	8.1.	Subject Inclusion Criteria (Part 1 and Part 2)	
	8.2.	Subject Exclusion Criteria (Part 1 and Part 2)	
	8.3.	Lifestyle Considerations	
	8.4.	3.4. Screening Failures	

## APL-9 APL9-COV-201 Protocol Amendment 3

9.		TREA	TMENT OF SUBJECTS	37
9.1. St 9.1.1.		Study	Interventions	
		1.	Study Drug Administration	37
	9.1.2.		Empiric Antibiotic Treatment for Possible Infection	
	9.2.	Prepar	ation, Handling, Storage, and Accountability	39
	9.3.	Measu	res to Minimize Bias: Randomization and Blinding	40
	9.3.	1.	Randomization	40
	9.3.2.		Blinding (Part 2 Only)	40
	9.4.	Treatm	ent Compliance	40
	9.5.	Conco	mitant Medications	40

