#### 9.1.1. Study Drug Administration

APL-9 is provided in sterile vials, each containing 180 mg of APL-9 in 6 mL buffer (30 mg/mL). Study drug infusion bags are prepared by an unblinded pharmacist at the study site by dilution of the study drug in isotonic saline for infusion and transferred to site personnel for administration to subjects according to their assigned randomization numbers. Two types of infusion bags containing APL-9 will be prepared:

- 50-mL bag containing 1 vial of APL-9 (ie, 180 mg of APL-9 in 50 mL)
- 250-mL bag containing 1 vial of APL-9 (ie, 180 mg of APL-9 in 250 mL)

Dosing of subjects receiving APL-9 either as open-label treatment or by random, blinded assignment must occur on Day 1, on the same day as randomization, and will be initiated with an IV infusion of 180 mg APL-9 in 50 mL of saline over a 10-minute period, followed within 1 hour by continuous infusion of 180 mg APL-9 in 250 mL saline at the rate of 15 mg/h (approximately 21 mL/h) until the end of study drug administration as follows:

• Part 1: at Day 7 or until or resolution of ARDS (PaO2/FiO2 ratio >300 mm Hg), whichever occurs earlier

• Part 2: at Day 7 or up to and including the approved treatment duration, discontinuation of respiratory support (supplemental oxygen or mechanical ventilation), or hospital discharge, whichever occurs latest

This results in the infusion of two 250-mL bags, each containing 180 mg of APL-9, every 24 hours.

Dosing of subjects randomly assigned to vehicle control must occur on Day 1, on the same day as randomization, and will be initiated with an IV infusion of 50 mL of saline over a 10-minute period followed immediately (and up to and including within 1 hour) by continuous infusion of approximately 21 mL of saline per hour until the end of study drug administration at Day 7 (or approved treatment extension), discontinuation of respiratory support (oxygen supplementation or mechanical ventilation), or hospital discharge, whichever occurs latest. This results in the infusion of 2 bags of 250 mL saline every 24 hours.

Research nurses or other appropriately qualified personnel will administer the IV infusions.

The pharmacists and investigator can change the size of the infusion bags in the event that 50-mL and 250-mL isotonic saline bags are in short supply if:

- the infusion rates of a 180-mg loading dose of APL-9 in the initial 10 minutes and 15 mg/h thereafter to subjects receiving APL-9 are maintained and

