- vehicle-only bags of identical size and appearance are given to the vehicle control group.

In the event that isotonic saline for infusion is not available, the pharmacists must contact Apellis Pharmaceuticals, Inc, to select an alternative vehicle.

The treatments are intended to continue to either Day 7 or until the subject no longer requires respiratory support (oxygen supplementation or mechanical ventilation) or is discharged from the hospital (whichever occurs later), except upon allowance by the DMC and by investigator discretion to administer treatment up to and including Day 21 (Part 2 only; extended treatment will be allowed only in subjects who still require respiratory support at Day 7 with an improved PaO2/FiO2 ratio of at least 20 mm Hg from baseline if ABG test results are available for comparison. If ABG test results are not available, an improvement in FiO2 of at least 4% in nonventilated patients (eg, those on nasal cannula) and 10% in mechanically ventilated patients is needed. FiO2 should be weaned following the site's protocol to keep oxygen saturation at 89% or above. Treatment beyond Day 7 and up to and including any DMC-approved extension will be at the discretion of the investigator. If treatment is interrupted for any reason for more than 24 hours, treatment may not be resumed.

A relapse of respiratory failure or ARDS due to COVID-19 must be reported as an AE. Under no circumstances can study drug be administered beyond the DMC-approved treatment window, and treatment may not be reinitiated if it is discontinued.

The SOC to be used at each study site will be determined by the investigator. A recent guideline for the treatment of critically ill patients with COVID-19 has been published and should be considered (CDC 2020).

Infusion-related reactions that occur during the administration of the 50- mL loading dose should be treated as follows:

- For mild infusion-related reactions: The 50 mL bag infusion time should be increased from 10 min to 20-40 min and the reaction should be monitored. Treatment with diphenhydramine may be required. The infusion time of the 250-mL bag should not be increased.
- For severe or persistent mild infusion-related reactions (instances in which the subject's symptoms do not respond to the increased infusion time): treatment should be discontinued, and the institution's emergency hypersensitivity protocol should be employed.

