## 10. DISCONTINUATION OF STUDY INTERVENTION AND SUBJECT DISCONTINUATION/WITHDRAWAL

#### **10.1.** Discontinuation of Study Intervention

Treatment with study drug (APL-9 IV or matching vehicle IV infusion) will terminate as follows:

- Part 1: at Day 7 or until or resolution of ARDS (PaO2/FiO2 ratio >300 mm Hg), whichever occurs earlier
- Part 2: at Day 7 or up to and including the approved treatment duration, discontinuation of respiratory support (supplemental oxygen or mechanical ventilation), or hospital discharge, whichever occurs latest

In Part 2, the DMC may decide to allow treatment with study drug beyond Day 7. If allowed by the DMC, study drug infusions can be extended at the discretion of the investigator beyond Day 7 up to and including Day 21. In Part 2, dosing may be extended only in subjects who still require respiratory support (oxygen supplementation or mechanical ventilation) at Day 7 with a PaO2/FiO2 ratio improved by at least 20 mm Hg from baseline if ABG test results are available for comparison. If ABG test results are not available, an improvement of FiO2 of at least 4% in nonventilated patients (eg, those on nasal cannula) and 10% in mechanically ventilated patients is needed. FiO2 should be weaned following the site's protocol to keep oxygen saturation at 89% or above. Treatment beyond Day 7 and up to and including any DMC-approved extension will be at the discretion of the investigator. However, study drug administration must end at the DMC-allowed maximal time point or upon the subject's discharge from the hospital. The time of transfer and termination of study drug treatment must be recorded in the subject's medical records and eCRF. If treatment is interrupted for any reason for greater than 24 hours, treatment may not be resumed.

In rare instances, it may be necessary for a subject to permanently discontinue study treatment (definitive discontinuation). The date of and reason for treatment discontinuation must be determined by the investigator and recorded in the subject's medical record and on the appropriate eCRF. If it is determined that there was more than one reason for the discontinuation, each reason should be documented in the source document and the most clinically relevant reason, as determined by the investigator, should be entered on the eCRF (see also Section 10.2).

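### The Part 2 stop rule takes the latest of three events and so contradicts the protocol's own limits on how long study drug may be given

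*Protocol*

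**What the plan says.** The rule. Section 7.1 runs Part 2 treatment "from Day 1 through Day 7, discontinuation of respiratory support (supplemental oxygen or mechanical ventilation), or hospital discharge, whichever occurs latest". SAP Section 3.1 repeats it. Section 9.1.1 gives it for the APL-9 arm, for the vehicle arm ("at Day 7 (or approved treatment extension), discontinuation of respiratory support (oxygen supplementation or mechanical ventilation), or hospital discharge, whichever occurs latest"), and again in a paragraph on intended duration ("until the subject no longer requires respiratory support (oxygen supplementation or mechanical ventilation) or is discharged from the hospital (whichever occurs later"). Section 10.1 ends Part 2 dosing at Day 7 or "the approved treatment duration, discontinuation of respiratory support (supplemental oxygen or mechanical ventilation), or hospital discharge, whichever occurs latest". Table 1 footnote a and two places in the Synopsis (the Part 2 design and the Part 2 study drug treatments) also carry it. That makes nine statements. The Synopsis design sentence is garbled in the text available here, so it is weak evidence of exact wording.

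The limits, in the same protocol:

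- Section 7.1, in the paragraph after the rule: dosing past Day 7 needs DMC approval, and "extended treatment will be allowed only in subjects who still require respiratory support (oxygen supplementation or mechanical ventilation) at Day 7", with an oxygenation gain. SAP Section 3.1 repeats this.
- Synopsis, Independent DMC: "Treatment duration in Part 2 may be maximally extended up to and including Day 21".
- Section 9.1.1: "Under no circumstances can study drug be administered beyond the DMC-approved treatment window, and treatment may not be reinitiated if it is discontinued".
- Section 10.1: "However, study drug administration must end at the DMC-allowed maximal time point or upon the subject's discharge from the hospital".

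**The concern.** A stop rule should give one day for each subject. Here the general rule takes the last of several events, while the limits take the first of two of them. For most courses of illness the two cannot both be followed.

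What is at stake is when to end a continuous infusion of an investigational C3 inhibitor. The prophylactic antibiotic is at stake too, because the Synopsis ties it to study drug. Sites that act on different sentences could stop on different days.

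**Working it through.** No power or error-rate calculation applies; this is a comparison of rules.

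**Inputs.** A = Day 7, or the DMC-approved extension day (at most 21) in a subject who qualifies (Sections 7.1 and 10.1; Synopsis, Independent DMC). W = day respiratory support ends. D = day of discharge.

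**Formulas.** Stop day under the rule as worded = max(A, W, D). Stop day under the limits = min(A, D).

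**Step 1, the plan's own figure.** The safety follow-up falls 30 days after the last dose and is capped at Study Day 51. A last dose on Day 21 gives 21 + 30 = 51, exactly the stated cap. So the follow-up calendar assumes that dosing never passes Day 21. This supports the limits but is not itself a dosing stop.

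**Step 2, when the two agree.** max(A, W, D) is at least A and at least D, while min(A, D) is at most A and at most D. They are equal only if D = A and W is no later than A. For A = 7, take all day pairs with W no later than D and both between Day 1 and Day 30: 30 × 31 / 2 = 465 pairs. Agreement needs D = 7 and W from 1 to 7, which is 7 pairs. The other 465 − 7 = 458 conflict. This counts combinations; it is not a probability.

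**Step 3, illustrations.** The days are chosen for illustration, not taken from the documents, and support is assumed to end by discharge.

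| Case | A | D | Rule: max | Limits: min | Gap |
|---|---|---|---|---|---|
| Early discharge, no extension | 7 | 4 | Day 7 | Day 4 | 3 days |
| Long stay, no extension | 7 | 14 | Day 14 | Day 7 | 7 days |
| Long stay, extension to Day 21 | 21 | 28 | Day 28 | Day 21 | 7 days |

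In the first case the literal rule runs the infusion for three days after the subject has left hospital. Section 9.1.2 handles that situation the other way: subjects who leave early are followed by telephone.

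**Step 4, the extension itself.** Under the literal rule, a subject still in hospital after Day 7 would stay on drug with no DMC decision and no eligibility test. The extension provisions would then have little left to do, so the rule and the extension provisions cannot both mean what they say.

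**Step 5, weaning.** W does not appear in min(A, D). When W is no later than D, max(A, W, D) = max(A, D), so W drops out there too. Under either reading, weaning alone does not end dosing.

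**Step 6, where each limit stands.** The Day 7 and Day 21 limits appear beside the rule in Section 7.1, the Synopsis and SAP Section 3.1. The absolute bar on dosing beyond the window is in Section 9.1.1 only, and the stop-at-discharge sentence is in Section 10.1 only.

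**The case against.** The strongest reply is that the specific limits override the general rule. The sentences in Sections 9.1.1 and 10.1 are worded as absolute stops. Section 7.1, the Synopsis and SAP Section 3.1 set out the duration limits beside the rule. The Synopsis and SAP Section 3.1 also presuppose that a subject who reaches the maximum duration must stop. Qualified staff give the drug under supervision, so an infusion after discharge is not realistic. Most of this stands: the intent is clear and points to the safe action. But no sentence says which text takes precedence. If the limits always win, the rule adds nothing, yet it is stated nine times.

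A reader might infer three stronger points, and the documents support none of them.

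- *Sections 7.1 and SAP 3.1 order dosing that only Sections 9.1.1 and 10.1 forbid.* Not so: those sections carry the duration limits and lack only the discharge stop and the absolute bar.
- *Stop days after weaning are ambiguous.* Not so: Step 5 shows that both readings continue after weaning. A stop at weaning comes from the wording that Amendment 3 replaced, which is no longer in force. During an extension the investigator may stop earlier, but that discretion is stated openly.
- *The Day 6 example in Table 1 footnote a proves a third rule.* It cannot arise in Part 2 if the shortest approved duration is Day 7. However, the column it explains also covers Part 1, where dosing can end before Day 7 when ARDS resolves. The example is weak evidence and merely needs correcting.

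**Conclusion.** The rule is wrong as written. Current operative text gives a Part 2 stop rule that the same protocol forbids following whenever discharge does not fall on the approved end day. In the illustrations the two readings differ by 3 to 7 days. How many subjects would be affected depends on length of stay, which the documents do not give.

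These are differences between readings of the text. A reader might infer that subjects would be overdosed, but the documents do not support that, because Sections 9.1.1 and 10.1 tell the site to stop. Nor is the analysis undermined: SAP Sections 5.6 and 7.1 work from actual dosing, and no endpoint definition or significance level uses the rule. The practical risk is limited to inconsistent conduct between sites.

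The conclusion rests on reading the rule's words in their ordinary sense and on no precedence clause existing in the text available. Figure 2 is not shown.

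**What to change.** Replace the rule in every place listed above, for both arms, with one sentence: *Part 2 dosing ends at the earliest of (a) Day 7, or the DMC-approved extension (at most Day 21) in subjects who qualify at Day 7; (b) hospital discharge; (c) death or permanent discontinuation.* Keep the investigator's discretion during an extension.

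Add a clause saying that weaning from respiratory support does not by itself end dosing, which is what the current text implies. Change the footnote a example to match, for instance to a subject discharged on Day 6.

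The same phrase sets the DMC review triggers at the 10th and 30th subjects (Synopsis; Protocol Sections 5.3, 7.1 and 12.7; Table 1 footnote a; SAP Section 3.1). As worded, a review can wait for discharge or the end of support after approved treatment is over. The sponsor should confirm that this is intended or align it with the new sentence.

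The cost is wording in the protocol and SAP Section 3.1, plus the sponsor's decision on the review triggers. No subjects, visits or analyses are added. The differing end-of-treatment visit timing in Section 11 and Table 1 footnote n is a separate minor point.
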